9.5.4.2 Reporting of Pregnancy and Exposure to Study Drug Through Breastfeeding

Any pregnancy in which the estimated date of conception is either before the last visit or within 28 days of last study treatment, or any exposure to study drug through breastfeeding during study treatment or within 28 days of last study treatment, must be reported.

If an adverse outcome of a pregnancy is suspected to be related to study drug exposure, this should be reported regardless of the length of time that has passed since the exposure to study treatment.

A congenital anomaly, death during perinatal period, an induced abortion, or a spontaneous abortion are considered to be an SAE and should be reported in the same time frame and in the same format as all other SAEs (see Reporting of SAEs [[Section 9.5.4.1](#)]).

Pregnancies or exposure to study drug through breastfeeding must be reported by fax or email as soon as possible but no later than 1 business day from the date the investigator becomes aware of the pregnancy. The contact information for the reporting of pregnancies and exposure to study drug through breastfeeding is provided in the Investigator Study File. The Pregnancy Report Form must be used for reporting. All pregnancies must be followed to outcome. The outcome of the pregnancy must be reported as soon as possible but no later than 1 business day from the date the investigator becomes aware of the outcome.

A subject who becomes pregnant must be withdrawn from study treatment.

Pregnancies in partners of male study subjects do not need to be reported. (revised per Amendment 03)

9.5.4.3 Reporting of Events Associated with Special Situations

9.5.4.3.1 REPORTING OF ADVERSE EVENTS ASSOCIATED WITH STUDY DRUG OVERDOSE, MISUSE, ABUSE, OR MEDICATION ERROR

AEs associated with study drug overdose, misuse, abuse, and medication error refer to AEs associated with uses of the study drug outside of that specified by the protocol. Overdose, misuse, abuse, and medication error are defined as follows:

Overdose	Accidental or intentional use of the study drug in an amount higher than the protocol-defined dose
Misuse	Intentional and inappropriate use of study drug not in accordance with the protocol
Abuse	Sporadic or persistent intentional excessive use of study drug accompanied by harmful physical or psychological effects
Medication error	Any unintentional event that causes or leads to inappropriate study drug use or subject harm while the study drug is in the control of site personnel or the subject.

All AEs associated with overdose, misuse, abuse, or medication error should be captured on the Adverse Event eCRF and also reported using the procedures detailed in Reporting of SAEs ([Section 9.5.4.1](#)) even if the AEs do not meet serious criteria. Abuse is always to be captured as an AE. If the AE associated with an overdose, misuse, abuse, or medication error does not meet serious criteria, it must still be reported using the SAE form and in an expedited manner but should be noted as nonserious on the SAE form and the Adverse Event eCRF.

Subjects will be monitored for AEs that may signal drug abuse potential during the Treatment Period and the first 4 weeks of the Follow-up Period. Examples of AEs that may signal drug abuse potential are provided in [Appendix 3](#). A detailed listing of AEs that may signal drug abuse potential is provided in the E2909-G000-301 eCRF Completion Guidelines. (revised per Amendment 03)

9.5.4.3.2 REPORTING OF STUDY-SPECIFIC EVENTS

Study-specific events (ocular herpes, new onset seizures, and symptomatic cerebral vasogenic edema), as detailed in [Section 9.5.1.5.2](#) should always be considered as serious important medical events and be entered on the Adverse Event eCRF and reported using the procedures detailed in Reporting of SAEs ([Section 9.5.4.1](#)), even if the study-specific event does not meet other serious criteria.

9.5.4.4 Expedited Reporting

The sponsor must inform investigators (or as regionally required, the head of the medical institution) and regulatory authorities of reportable events, in compliance with applicable regulatory requirements, on an expedited basis (ie, within specific time frames). For this reason, it is imperative that sites provide complete SAE information in the manner described above.

9.5.4.5 Breaking the Blind

In the case of a medical emergency where the appropriate treatment of the subject requires knowledge of the study treatment given, the investigator may break the randomization code for an individual subject. In all such cases, the AE necessitating the emergency blind break will be handled as an SAE in accordance with the procedures indicated above. Any broken code will be clearly justified and documented. The medical monitor must be notified immediately of the blind break.

9.5.4.6 Regulatory Reporting of AEs

AEs will be reported by the sponsor or a third party acting on behalf of the sponsor to regulatory authorities in compliance with local and regional law and established guidance. The format of these reports will be dictated by the local and regional requirements.

All studies that are conducted within any European country will comply with European Good Clinical Practice Directive 2005/28/EC and Clinical Trial Directive 2001/20/EC. All SUSARs will be reported, as required, to the competent authorities of all involved European member states.

9.5.5 Completion/Discontinuation of Subjects

A subject may elect to withdraw from the study at any time for any reason. All subjects who discontinue study drug early for any reason will undergo an ED Visit within 7 days of their last dose of study drug (see [Section 9.1.2.2](#)). In addition, Follow-up Visits will be scheduled 4 and 12 weeks after the last dose of study drug (Visit 14 and Visit 15, respectively) (see [Section 9.1.2.2](#)). These Follow-up Visits will be conducted to monitor efficacy and safety parameters after early withdrawal from the study or discontinuation of study drug. See [Table 5](#) for full details of the assessments to be performed at these visits.

All subjects who discontinue study drug before reaching 12 months of treatment will also be asked to return to the clinic for a 12 month clinical assessment and then again at 24 months. Subjects who discontinued treatment between 12 and 24 months of treatment will be asked to return to the clinic for a 24-month clinical assessment. Subjects who discontinue early from study drug are considered “on study” as long as they continue to return for their clinical assessments at 12 and 24 months as outlined above, at which efficacy and quality of life will be assessed along with concomitant medications and AEs. However, subjects who discontinue study drug early are not considered to have ‘completed’ the study as a final Subject Disposition. A subject removed from the study for any reason may not be replaced.

The investigator will promptly explain to the subject involved that the study will be discontinued for that subject and provide appropriate medical treatment and other necessary measures for the subject. A subject who has ceased to return for visits will be followed up by mail, phone, or other means to gather information such as the reason for failure to return, the status of treatment compliance, the presence or absence of AEs, and clinical courses of signs and symptoms.

The primary reasons for early withdrawal from the study are: AE, lost to follow up, subject choice, withdrawal of consent, pregnancy, study terminated by sponsor, and other. The secondary reasons for early withdrawal from the study are: AE, subject choice, and other.

The primary reasons for early discontinuation from the study drug are: AE, subject choice, pregnancy, inadequate therapeutic effect, and other. The secondary reasons for early discontinuation from the study drug are: AE, subject choice, inadequate therapeutic effect, and other.

9.5.6 Abuse or Diversion of Study Drug

AEs associated with abuse or diversion will be appropriately reported as AEs and monitored per [Section 9.5.1.5.1](#). Abuse is always to be captured as an AE.

During the study, the investigator should be aware of the possibility of abuse or diversion of study drugs and should report any concern about mishandling, abuse, loss, theft, or diversion of study drugs by completing the Abuse or Diversion of Study Drug eCRF.

9.5.7 Confirmation of Medical Care by Another Physician

The investigator will instruct subjects to inform site personnel when they are planning to receive medical care by another physician. At each visit, the investigator will ask the subject whether he or she has received medical care by another physician since the last visit or is planning to do so in the future. When the subject is going to receive medical care by another physician, the investigator, with the consent of the subject, will inform the other physician that the subject is participating in the clinical study.

9.6 Data Quality Assurance

This study will be organized, performed, and reported in compliance with the protocol, standard operating procedures, working practice documents, and applicable regulations and guidelines. Site audits will be made periodically by the sponsor's or the CRO's qualified compliance auditing team, which is an independent function from the study team responsible for conduct of the study.

9.6.1 Data Collection

Data required by the protocol will be collected on the eCRFs and entered into a validated data management system that is compliant with all regulatory requirements. As defined by ICH guidelines, the CRF is a printed, optical, or electronic document designed to record all of the protocol-required information to be reported to the sponsor on each study subject.

Data collection on the eCRF must follow the instructions described in the CRF Completion Guidelines. The investigator has ultimate responsibility for the collection and reporting of all clinical data entered on the eCRF. The investigator or designee as identified on Form FDA 1572 (where applicable) must sign the completed eCRF to attest to its accuracy, authenticity, and completeness.

Completed, original eCRFs are the sole property of Eisai and should not be made available in any form to third parties without written permission from Eisai, except for authorized representatives of Eisai or appropriate regulatory authorities.

9.6.2 Clinical Data Management

All software applications used in the collection of data will be properly validated following standard computer system validation that is compliant with all regulatory requirements. All data, both eCRF and external data (eg, laboratory data), will be entered into a clinical system.

Electronic source (eSource) methodology may be used for some of the clinical efficacy and HRQoL assessments performed in this study.

9.7 Statistical Methods

All statistical analyses will be performed by the sponsor or designee. Statistical analyses will be performed using SAS software or other validated statistical software as required.

All statistical tests will be based on the 5% (2-sided) level of significance, unless specified.

For statistical methods specific to the Extension Phase, refer to [Appendix 5 in Section 12](#).

9.7.1 Statistical and Analytical Plans

All statistical analyses will be performed by the Sponsor or designee after the study is completed and the database is locked and released for unblinding. All statistical analyses will be performed based on the pooled data from 2 studies (E2609-G000-301 and E2609-G000-302). The analyses will also be performed within each study to confirm the trend of the efficacy and biomarker endpoints unless specified. (revised per Amendment 05)

9.7.1.1 Study Endpoints

9.7.1.1.1 PRIMARY ENDPOINT

The primary endpoint of the study is:

- Change from baseline in the CDR-SB at 24 months in the combined studies (revised per Amendment 05)

9.7.1.1.2 SECONDARY ENDPOINTS

The key secondary endpoints of the study are as follows (revised per Amendment 05):

- Change from baseline in ADCOMS at 24 months in the combined studies
- Change from baseline in amyloid PET SUVR at 24 months for brain amyloid levels in the combined studies
- Change from baseline in amyloid PET SUVR at 24 months for brain amyloid levels in the individual studies

The other secondary endpoints of the study are as follows (revised per Amendment 05):

- Change from baseline in the CDR-SB at 24 months for subjects enriched by baseline PET SUVR, eg, between 1.2 and 1.6, in the combined studies
- Change from baseline in the ADCOMS at 24 months for subjects enriched by baseline PET SUVR, eg, between 1.2 and 1.6, in the combined studies
- The rate of change over time (mean slope) based on CDR-SB score over 24 months in the combined studies
- Time to worsening of CDR scores by 24 months (eg, the worsening of global CDR score is defined as an increase from baseline by at least 0.5 points on the global CDR scale on 2 consecutive scheduled visits at which global CDR is undertaken) in the combined studies

- Time to conversion to dementia by 24 months for subjects who were not clinically staged as dementia at Baseline based on clinical diagnosis in the combined studies
- Change from baseline in CDR-SB at 27 months (ie, 24 months of treatment plus 3 months posttreatment follow-up) in the combined studies
- Change from baseline in ADAS-cog14, MMSE, and FAQ at 24 months in the combined studies
- Change from baseline in ADAS-cog14 Word List (immediate recall and delayed recall) at 24 months in the combined studies

9.7.1.1.3 BIOMARKER ENDPOINTS

The biomarker endpoints of the study are:

- Change from baseline in tau PET signal at 24 months (revised per Amendment 04)
- Change from baseline in CSF biomarkers t-tau and p-tau at 24 months
- Change from baseline in CSF amyloid biomarkers $A\beta(1-42)$, and $A\beta(1-x)$ at 24 months (revised per Amendment 03)
- Change from baseline in plasma amyloid biomarker (eg, $A\beta(1-x)$) at all assessments (revised per Amendment 05)
- Change from baseline in potential plasma and CSF biomarkers of AD (eg, NFL, VILIP1, YKL-40, and Ng) (revised per Amendment 05)
- Change from baseline in total hippocampal volume at 24 months using vMRI
- Change from baseline in the preservation of connectivity on fMRI at 24 months

9.7.1.1.4 EXPLORATORY ENDPOINTS

The exploratory endpoints of the study are:

- Time to change of concomitant AD treatment (ie, dose increase and/or initiation of treatment with AChEI or memantine after randomization) by 24 months
- The proportion of subjects at 24 months who received dose increases and/or initiation of treatment with AChEI or memantine after randomization
- The rate of change over time (mean slope) based on NPI-10 item score over 24 months
- Change from baseline in NPI-10 item at 24 months
- Change from baseline in EQ-5D (subject self-reported, study partner self-reported, and subject measured by proxy) and QOL-AD (subject and study partner) at 24 months
- Change from baseline in Zarit's Burden Interview at 24 months

9.7.1.2 Definitions of Analysis Sets

- The Randomized Set is the group of subjects who are randomized to study drug.

- The Safety Analysis Set is the group of subjects who receive at least 1 dose of study drug and have at least 1 postdose safety assessment.
- The Full Analysis Set (FAS) is the group of randomized subjects who receive at least 1 dose of study drug and have baseline and at least 1 postdose primary efficacy measurement.
- The Per Protocol Analysis Set (PPS) is the subset of subjects in the FAS who sufficiently comply with the protocol. The PP Analysis Set will be used to conduct a sensitivity analysis of the primary efficacy endpoint. Details of the evaluability criteria will be determined before database lock and treatment unblinding, and will be specified in the statistical analysis plan.
- The PK Analysis Set is the group of subjects with at least 1 quantifiable elenbecestat plasma concentration with a documented dosing history.
- The PD Analysis Set is the group of subjects who have sufficient PD data to derive at least 1 PD parameter.

9.7.1.3 Subject Disposition

The number of subjects screened, the number (percent) of subjects who failed screening, and the reasons for screen failure will be summarized, based on data reported on the Screening Disposition eCRF. The distribution of the number of randomized subjects enrolled by each site will be summarized for each randomized treatment group. The primary reasons for screen failures (did not meet inclusion or met exclusion criteria, AE, lost to follow-up, withdrawal of consent, and other) will be presented.

Study Completion: the number (percent) of randomized and treated subjects who completed the study and who discontinued from the study will be summarized according to the primary reason for discontinuation and secondary reason(s) for discontinuation, based on data reported on the Subject Disposition (Study Phase) CRF. The number (percent) will be presented by treatment group and total for subjects; randomized, not treated, treated, who completed the study, and discontinued from the study. The primary reasons for early withdrawal from the study are: AE, lost to follow-up, subject choice, withdrawal of consent, pregnancy, study terminated by sponsor, and other. The secondary reasons for early withdrawal from the study are: AE, subject choice, and other.

Completion of Study Treatment: the number (percent) of randomized and treated subjects who completed study drug and who discontinued from study drug will be summarized according to the primary reason for discontinuation and also according to secondary reason(s) for discontinuation, based on data reported on both the Subject Disposition (Study Phase) eCRF and ED from Study Drug eCRF. The number (percent) will be presented by treatment group and total for subjects; randomized, not treated, treated, who completed study drug, and discontinued from study drug. The primary reasons for early discontinuation from the study drug are: AE, subject choice, pregnancy, inadequate therapeutic effect, and other. The secondary reasons for early discontinuation from the study drug are: AE, subject choice, inadequate therapeutic effect, and other.

9.7.1.4 Demographic and Other Baseline Characteristics

Demographic and other baseline characteristics for the Safety Analysis Set and FAS will be summarized for each treatment group using descriptive statistics. Continuous demographic and baseline variables include age, CDR scores, ADAS-cog14, MMSE and FAQ; categorical variables include sex, age group (equal or less than 65 years, age greater than 65 years), race, ethnicity, region, *ApoE4* genotype, prior treatment with AChEIs or memantine (no or yes), and clinical subpopulation (MCI due to AD or the early stages of mild AD).

9.7.1.5 Prior and Concomitant Therapy

All investigator terms for medications recorded in the eCRF will be coded to an 11-digit code using the World Health Organization Drug Dictionary (WHO DD) (Mar 2014). The number (percentage) of subjects who took prior and concomitant medications will be summarized on the Safety Analysis Set by treatment group, Anatomical Therapeutic Chemical class, and WHO DD preferred term (PT). Prior medications will be defined as medications that stopped before the first dose of study drug. Concomitant medications will be defined as medications that (1) started before the first dose of study drug and were continuing at the time of the first dose of study drug, or (2) started on or after the date of the first dose of study drug up to the date of the last dose. All medications will be presented in subject data listings.

Medications taken within the 12-week Follow-up Period will also be recorded.

9.7.1.6 Efficacy Analyses

The FAS will be used as the primary population for all efficacy analyses, while the PPS will be used as the supportive population.

9.7.1.6.1 PRIMARY EFFICACY ANALYSIS

The primary analysis will be based on an intent to treat philosophy without regard to adherence to treatment. The primary analysis of the change from baseline in CDR-SB at 24 months will be performed to compare elenbecestat 50 mg per day versus placebo using a linear mixed effects model for repeated measures (MMRM) on the FAS. The MMRM model will include fixed effects of treatment group, visit, treatment group by visit interaction, baseline CDR-SB, baseline CDR-SB by visit interaction, and randomization stratification variables (ie, region [7 levels], clinical dementia [yes, no], and concurrent AD medication use at randomization [Visit 2] [yes, no]). *ApoE4* status may be included in the model if appropriate. (revised per Amendment 05) An unstructured covariance matrix will be employed to model the covariance of within subject effect; if MMRM fails to converge then a covariance structure with fewer parameters from the following list will be employed according to the prespecified order in the list until the MMRM converges. The list of covariance structure will include Heterogeneous Toeplitz, Toeplitz, Heterogeneous Compound Symmetry, and Compound Symmetry. This primary analysis will include all observed post baseline data of the change from baseline in CDR-SB without imputation of missing values. The treatment effect for elenbecestat versus placebo will be compared at

24 months based on MMRM model. The LS means and difference in LS means between elenbecestat treatment group and placebo, and corresponding 95% CI will be presented.

The null hypothesis is that there is no difference in the mean change from baseline in CDR-SB at 24 months between elenbecestat 50 mg per day and placebo. The corresponding alternative hypothesis is that there is a difference in the mean change from baseline in CDR-SB at 24 months between elenbecestat 50 mg per day and placebo.

The primary analysis will be repeated to minimize the impact of change in concomitant AD medications where efficacy data after initiation of new AD medications and increase of current AD medications will be censored.

The following sensitivity analysis will be conducted to evaluate the impact of missing data: the primary endpoint will be analyzed using ANCOVA after multiple imputation. The ANCOVA model will include baseline CDR-SB as a covariate, with treatment group and randomization stratification variables as factors. *ApoE4* status may be included in the model if appropriate. Additional sensitivity analyses will be performed to assess the robustness of the missing at randomization assumption in the primary MMRM model.

Subgroup analysis (eg, stratification factors and *ApoE4* status) and additional sensitivity analysis for the primary endpoint will be performed as appropriate. (revised per Amendment 05)

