Time to worsening of CDR scores by 24 months will be analyzed on the FAS using Cox regression model for treatment effect adjusting for randomization stratification factors. ApoE4 status may be included in the model if appropriate. (revised per Amendment 05) Time to worsening of a CDR score is defined as time from randomization to worsening of the CDR score (ie, the first worsening in 2 consecutive scheduled visits). For subjects whose CDR scores have not worsened by the end of the Treatment Period of the Core Study, the time to worsening of the CDR score will be censored at the date of last CDR assessment for these subjects.

Time to conversion to dementia for subjects who were not clinically staged as dementia at Baseline based on clinical diagnosis will be analyzed on the FAS using Cox regression model for treatment effect adjusting for randomization stratification factors. ApoE4 status may be included in the model if appropriate. (revised per Amendment 05) Proportion of subjects with dementia diagnosis at 24 months will be estimated using Kaplan—Meier method based on time to conversion to dementia based on clinical diagnosis. Time to conversion to dementia for subjects who were not clinically staged as dementia at Baseline based on clinical diagnosis is defined as time from randomization to conversion to dementia based on clinical diagnosis. For subjects without clinical dementia by the end of study, the time to conversion to dementia based on clinical diagnosis will be censored at the date of last dementia diagnosis.

The other continuous secondary efficacy endpoints as defined above will be analyzed using the same MMRM model as the primary efficacy analysis to compare elenbecestat 50 mg per day versus placebo on the FAS, using baseline value corresponding to the response variable in the model.

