9.7.2 Determination of Sample Size

The sample size for this study is estimated for comparison of elenbecestat versus placebo with respect to a pooled analysis of studies E2609-G000-301 and E2609-G000-302 for the change from baseline in CDR-SB at 24 months. Based on the available data from the placebo group in Study BAN2401-G000-201 (a recently completed study with a comparable subject population), the mean and the standard deviation of the change from baseline in CDR-SB at 24 months in the placebo group are assumed to be 1.46 and 2.05, respectively, instead of 1.75 and 2.05, which are originally assumed by the available data from ADNI (of amyloid positive, MMSE equal or greater than 24, late MCI [global CDR=0.5, CDR memory box \geq 0.5]). Therefore, assuming a 25% reduction in the mean change from baseline CDR-SB at 24 months for elenbecestat compared to placebo with common standard deviation of 2.05 and 30% dropout rate, a total sample size of 1900 subjects, 950 subjects in each treatment group, will be required to detect the treatment difference between elenbecestat and placebo using a 2-sample t test with 90% power at a significance level of 2 sided alpha =0.05.

The pooled data from 2 studies (E2609-G000-301 and E2609-G000-302) will comprise the total sample size of approximately 1900 subjects. At least 850 subjects will be randomized in each study. (revised per Amendment 05)

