
Pooling of study 301 and 302 analysis, with decreased subjects and sites in each study
	
Sample size re-estimation indicated the requirement for 1900 subjects compared with the original 1330 subjects per study. Studies will be combined to achieve the required numbers.
	
Synopsis
 
 • Site(s) • Core Study Objectives • Study Design • Number of Subjects • Statistical Methods 
Section 6 Section 8.1 Section 8.2 Section 9.1 Section 9.2.1 Section 9.3 Section 9.7.1.1 Section 9.7.2

Study 202 summary of safety
	
Emerging clinical data
	
Section 7.1

Revisions to Version 5.0

New version/date: Version 6.0/21 Jan 2019 (per Amendment 05)

Change	Rationale	Affected Protocol Sections
and efficacy added and its Extension Phase, exposure	indicating acceptable safety and signals of clinical efficacy	Section 9.4.4
Key secondary objectives defined	Three key secondary objectives have been defined from the multiple secondary objectives, indicating those of most importance that will be tested in a hierarchical manner if the primary objective is significant.	Synopsis 
 • Core Study Objectives • Statistical Methods Section 8.2 Section 9.7.1.1.2 Section 9.7.1.6.2
Added Alzheimer’s Disease Composite Score (ADCOMS) as a secondary objective for the Core Study	This novel endpoint has been included, aimed at optimizing sensitivity to disease progression over time in the MCI population, allowing earlier detection of clinical change.	Synopsis 
 • Core Study Objectives, Secondary Objectives • Assessments • Study Endpoints Section 8.2 Section 9.2.1 Section 9.2.3 Section 9.5.1.3.1 Section 9.7.1.1.2 Section 9.7.1.6.2
Added of CDR-SB and ADCOMS enriched by baseline amyloid PET SUVR as a secondary objective for the Core Study	Elenbecestat may be more effective when amyloid reaches a minimum level but before too much is on board	Synopsis 
 • Core Study Objectives, • Study Endpoints Section 8.2 Section 9.7.1.1.2 Section 9.7.1.6.2
Added a biomarker objective and endpoints for the Core Study	Clarification	Synopsis 
 • Core Study Objectives • Biomarker Endpoints • Analyses for Biomarker Endpoints Section 8.2 Section 9.7.1.1.3 Section 9.7.1.7.3
Revised country list	To reflect that South Africa is a participating country	Synopsis 
 • Study Design Section 9.1

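### The primary model pools two separately randomised studies but contains no study factor

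*Protocol*

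**What the plan says.** Protocol 9.7.1 states: "All statistical analyses will be performed based on the pooled data from 2 studies (E2609-G000-301 and E2609-G000-302"). The primary endpoint in 9.7.1.1.1 is "Change from baseline in the CDR-SB at 24 months in the combined studies". Section 9.7.2 adds: "At least 850 subjects will be randomized in each study".

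Section 9.7.1.6.1, repeated in the synopsis, gives the MMRM "fixed effects of treatment group, visit, treatment group by visit interaction, baseline CDR-SB, baseline CDR-SB by visit interaction, and randomization stratification variables". The last item is closed by an 'ie' list: "randomization stratification variables (ie, region [7 levels], clinical dementia [yes, no], and concurrent AD medication use at randomization [Visit 2] [yes, no"]. The only further covariate the text allows is ApoE4, which "status may be included in the model if appropriate". Study is not named.

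The other models follow the same pattern:
- The ANCOVA after multiple imputation (9.7.1.6.1) uses baseline, treatment and the stratification variables.
- The key secondary MMRMs (9.7.1.6.2) reuse the primary model.
- The slope model (9.7.1.6.2) uses treatment, baseline, the stratification variables and time terms.
- The time-to-event endpoints (9.7.1.6.2) are analysed "using Cox regression model for treatment effect adjusting for randomization stratification factors".

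Study enters only through separate within-study runs meant to confirm the trend (9.7.1), and through the within-study amyloid PET analysis among the key secondaries (9.7.1.6.2).

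**The concern.** When subjects were randomised within two studies and the data are then pooled, study is a design factor like the stratification variables the model already carries. Without it, a between-study difference in decline goes into the residual, and a difference between studies in the share on active treatment leaks into the treatment estimate.

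The revision history suggests how the gap arose. Before Amendment 05 the studies were sized separately at 1330 each; the amendment's rationale reads "Studies will be combined to achieve the required numbers". Its list of body sections affected by pooling includes 9.7.1.1 and 9.7.2 but not 9.7.1.6, where the models are. The same amendment did edit the model paragraph, to add optional ApoE4. The log only explains the gap; the defect lies in the current text.

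At stake is the specification of the only primary test, whose model also feeds the key secondary hierarchy.

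**Working it through.** **Inputs from 9.7.2.** Placebo mean change 1.46, SD 2.05, 25% reduction, 30% dropout, two-sided alpha 0.05, 90% power, 950 per arm. The planned effect is 0.25 × 1.46 = 0.365. Completers per arm: 950 × 0.7 = 665.

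**The plan's own figure.** n per arm = 2 × (1.960 + 1.282)² × 2.05² / 0.365² = 663. Dividing by 0.7 gives 948 per arm, 1896 in total. The exact t test gives 664, then 949, 1898 in total. The stated 1900 reproduces, and power at 665 per arm is 90.1%.

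**Assumptions.** D is the between-study difference in mean 24-month change that remains after the other covariates. The documents give no value, so 0 to 1.0 points is an assumed range. The two studies are taken as equal in size with 1:1 allocation in each, 2.05 is taken as the within-study SD, and a single time point stands in for the MMRM.

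**Effect of leaving study out.**
- SD seen by the model: S = √(2.05² + D²/4).
- True standard error: 2.05 × √(2/665). Standard error used by the model: S × √(2/665).
- Type I error: 2 × [1 − Φ(1.96 × S/2.05)].
- Power: Φ[(0.365 − 1.96 × model SE) / true SE].

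| D (assumed) | S | Type I error, no study term | Power, no study term | Power, with study |
|---|---|---|---|---|
| 0 | 2.0500 | 0.0500 | 90.1% | 90.1% |
| 0.3 | 2.0555 | 0.0494 | 90.0% | 90.1% |
| 0.5 | 2.0652 | 0.0483 | 89.8% | 90.1% |
| 0.75 | 2.0840 | 0.0463 | 89.5% | 90.1% |
| 1.0 | 2.1101 | 0.0437 | 89.1% | 90.1% |

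A simulation (1330 completers, 10,000 runs per scenario) agrees. At D = 1.0, type I error was 0.045 without study and 0.052 with it, and power 89.2% and 90.4%. The Monte Carlo standard error of the type I figures is about 0.002.

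**Bias.** With active shares p₁ and p₂ in two equal-sized studies, the bias is D × [p₂/(p₁+p₂) − (1−p₂)/(2−p₁−p₂)]. With exact 1:1 in each study it is 0. With an assumed 52% and 48% it is D × (0.48 − 0.52) = −0.04 × D. In size that is 0.012 points at D = 0.3 and 0.04 points at D = 1.0, or 3% and 11% of 0.365.

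**Cost of the term.** CDR is rated every 3 months to month 24, so there are 8 visits. Study plus study-by-visit adds 1 + 7 = 8 parameters.

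**The case against.** **The covariate list could be left to the SAP.** It could have been, but the protocol does not defer it. It enumerates the terms and closes the list, so an SAP that follows it would omit study.

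**The studies are near-twins, so D should be small.** This stands in part. Section 9.2.1 describes them jointly, with the same population, dose, control and duration, and the revision history calls them identical. The model already adjusts for region, dementia stage, medication and baseline by visit. D = 1.0 would be 68% of the assumed placebo decline (1.0/1.46), so the upper end is generous. Region does not replace study, however: nothing shown confines a region to one study.

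**Randomisation within each study is an inference.** It is, from the per-study minimum in 9.7.2 and from 9.4.3, which describes a scheme for this study. The Study 301 protocol is not shown. Nothing in the text suggests a shared list.

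**Consistency between studies is already examined.** This stands. Within-study analyses are planned, and within-study amyloid PET is a key secondary. A reader might infer that poolability goes unchecked and that a formal treatment-by-study test is needed. The documents do not support the first, and the test would be weak. With 332.5 completers per arm per study, the standard error of the difference between the two effects is √2 × 2.05 × √(2/332.5) = 0.225. Power to separate a full effect (0.365) in one study from none in the other is about Φ(0.365/0.225 − 1.96) = 37%. A study main effect says nothing about poolability either.

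**ApoE4.** A reader might add the optional ApoE4 covariate to this point. That is a separate question about covariate choice, with no size established here, and it lends no weight to this one.

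**Conclusion.** The point holds as a specification gap. The protocol pools two studies for its only primary test and fixes a model that omits the study factor, in the MMRMs and in the ANCOVA, slope and Cox models.

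Its size is small. Over the assumed D of 0 to 1.0 points, type I error stays between 0.044 and 0.050 and the power loss is at most about 1 percentage point. Bias is nil under 1:1 allocation in each study, and about 0.01 to 0.04 points under an assumed 52%/48% split with D from 0.3 to 1.0. Allocation is only approximately 1:1 (9.1), and with 30% dropout the month-24 balance within each study is not guaranteed, so a small bias cannot be excluded.

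A reader might infer that the error rate is inflated or that 1900 subjects are too few. Neither follows: the omission errs on the conservative side, and the sample size reproduces.

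**What to change.** In 9.7.1.6.1, 9.7.1.6.2 and the synopsis:
- Add study (301 or 302) and study-by-visit as fixed effects in the primary MMRM and every other pooled MMRM. Study-by-visit is needed because a study main effect alone removes only a shift common to all visits, whereas the comparison is made at month 24.
- Add study as a factor to the multiple-imputation ANCOVA and the slope model.
- Stratify the Cox models by study.
- Optionally, report the treatment-by-study estimate at month 24 with its confidence interval, as description beside the planned within-study analyses and not as a gate for pooling.

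The within-study runs need no study term. The cost is a sentence or two of text and a few degrees of freedom out of about 1900 subjects; the sample size is unchanged. The change should be made before unblinding, since a study term added afterwards could look data-driven.
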